### Analysis Methods

We summarize by arm the demographic and clinical characteristics of participants in the PushCon study using descriptive statistics but, following convention, do not compare characteristics between arms using statistical tests. To examine differential dropout by arm, affecting Week-16 survey outcomes only, we compare characteristics of participants with and without missing outcomes using chi-square or Wilcoxon rank-sum tests.

To analyze study outcomes, we used generalized estimating equation (GEE) models to estimate the mean (95% CI) ratio of arm-specific rates (for binomial or count outcomes) or geometric means (for continuous outcomes) and to generate 2-sided p-values, while accounting for correlated outcomes within study clinics. For longitudinal outcomes, assessed at baseline (after consent but before randomization; Week 0) and at the end of the intervention period (Week 16), we fit time and time\*arm as fixed effects, and nest correlated outcomes within study clinics; for cross-sectional outcomes we exclude the time effect from the model. In the setting of RCTs, the constrained longitudinal data analysis (cLDA) approach, used here, estimates a common mean across arms at baseline; in contrast, the LDA approach would include a fixed effect for arm to estimate distinct mean outcomes at baseline. The cLDA model is equivalent to the ANCOVA model when no data are missing; however, participants with some missing values, for example, at follow-up only, contribute to the cLDA model but not the ANCOVA model, increasing the cLDA's relative power.

*Receipt of guideline-recommended care* was calculated as a single proportion that can be modeled cross-sectionally. Each participant's outcome arises from a ratio of two counts,  $p_{care} = x/d$ , where  $d$  is the number of gaps in care noted over the 12-month pre-baseline (denominator, see Appendix A), and  $x$  is the number of these gaps that were noted as addressed during the 16-week intervention (numerator). To estimate the rate ratio (RR) (95% CI) we modeled  $x$  as a function of arm, specified a negative binomial distribution for  $x$  and used a log link with  $\log(d)$  as an offset.

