*Receipt of all guideline-recommended medications* is a binary longitudinal outcome. All medications recommended by GOLD/GINA guidelines for each participant were identified prior to the start of the study. The outcomes at Week 0 (using EHR data the 12 months prior to randomization) and at Week 16 (using EHR data from the 16-week intervention period) are scored  $y=1$ , if all were prescribed, and  $y=0$ , otherwise. Using a constrained longitudinal data analysis (cLDA) approach, which estimates equal rates by arm at baseline, we modeled  $y$  as a function of time and the time\*arm interaction, specified that  $y$  is binomial, and used a log link to estimate RRs at Week 16. Other binomial outcomes modeled analogously.

The *Saint George Respiratory Questionnaire*, a patient-reported outcome, is also measured longitudinally. It consists of 51 items in three domains: symptoms, activity, and impact, and has a total **score** ranging from 0 to 100, with higher scores indicating greater disability. The analysis method is the same for the overall score and its domains. Using the cLDA approach, we modeled  $z$  as a function of time and time\*arm, used a log link, and specified that  $y$  has a negative binomial distribution. The model estimates geometric means (95% CI) and estimates the relative mean (RM) (95% CI) to compare the HC and UC arms at Week 16. Another outcome using this model is *PACIC*.

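### As described, with correlation only within clinics, the Week-16 survey contrast is in effect a comparison of responders, open to bias if dropout depends on baseline severity differently by arm

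*Combined protocol and SAP*

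**What the plan says.** All statements are in Analysis Methods of the combined protocol and SAP.

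- Estimator: "we used generalized estimating equation (GEE) models to estimate the mean (95% CI) ratio of arm-specific rates" (or geometric means, for continuous outcomes).
- Correlation: the models serve "to generate 2-sided p-values, while accounting for correlated outcomes within study clinics". For outcomes measured at both visits, the fixed effects are time and time-by-arm, and the plan will "nest correlated outcomes within study clinics". It names no working correlation and never mentions correlation between one participant's two visits.
- Constraint: the cLDA approach "estimates a common mean across arms at baseline". The plan calls it equivalent to ANCOVA when data are complete, and more powerful when they are not, because "participants with some missing values, for example, at follow-up only, contribute to the cLDA model but not the ANCOVA model".
- SGRQ and its domains: a log-link negative binomial model that "estimates the relative mean (RM) (95% CI) to compare the HC and UC arms at Week 16". PACIC uses the same model, and other binomial outcomes are handled analogously.
- Missing data: the aim is given as "To examine differential dropout by arm, affecting Week-16 survey outcomes only". A single step is described for that aim: "we compare characteristics of participants with and without missing outcomes using chi-square or Wilcoxon rank-sum tests". No missingness assumption, weighting, imputation, baseline covariate or sensitivity analysis is stated, and nothing is said to follow from the comparison.

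**The concern.** The plan credits its model with two properties, ANCOVA equivalence and extra power from participants who lack follow-up. Both presuppose a link between a participant's baseline and Week-16 scores. In a model with time and time-by-arm terms alone, only the within-participant correlation can supply that link, and the text describes correlation only at clinic level.

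Without the link, nothing offsets selective non-response at Week 16. Selection that differs by arm is plausible: under the HC arm section, coached participants have a check-in call at least every 3 weeks and at least 5 contacts, while usual-care participants have no such scheduled contact. Any resulting bias would enter every patient-reported comparison, and the confidence interval would not show it.

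The dropout check would not reliably reveal the problem. It is introduced as examining dropout by arm, but as worded it compares participants with and without outcomes across both arms together, so opposite patterns in the two arms could cancel.

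**Working it through.** The documents give no SD, dropout rate or power calculation, so there is no figure of the plan's own to reproduce.

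**Inputs from the documents:** ten clinics (Setting); 1:1 randomization within clinic (Recruitment, enrollment, and randomization); 165 patients assigned to the coach (HC arm section); one baseline and one 16-week survey (Data Collection); model terms as above.

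**Assumed inputs:** SGRQ mean 50, SD 20, correlation between visits 0.7, clinic ICC 0.03, about 20% dropout, no true effect (relative mean 1.00).

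**Step 1: what the model estimates.** The mean model is log μ = b0 + b1·time + b2·time·arm. Three parameters describe three cells: pooled baseline, UC Week 16 and HC Week 16. With an independence working correlation, each fitted mean equals the observed mean of its cell, so

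exp(b2) = (mean of HC responders) / (mean of UC responders).

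Baseline-only participants enter the first cell only. An exchangeable correlation by clinic changes this very little (Step 3).

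**Step 2: size by hand.** Let the dropout probability be p = expit(−1.5 + 0.7·s), with s the standardized baseline score. For normal s, mean p = 0.203 and mean p(1−p) = 0.150. The responders' baseline shift is

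−0.7 × 0.150 / (1 − 0.203) = −0.132 SD, or −0.132 × 20 = −2.64 points.

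Carried to Week 16: −2.64 × 0.7 = −1.85 points.

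- Dependence in HC only: (50 − 1.85)/50 = 0.963.
- Opposite directions by arm: (50 − 1.85)/(50 + 1.85) = 0.929.

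**Step 3: simulation of the described GEE.** 150 replicates, 10 clinics of 34 participants, log link with negative binomial variance. Monte Carlo error is about 0.003-0.004. Entries are mean relative means (truth 1.00); IPW is inverse-probability-of-response weighting on baseline score by arm.

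| Dropout mechanism | Independence, clinic | Exchangeable, clinic | Exchangeable, participant | IPW |
|---|---|---|---|---|
| Random, 20% | 1.005 | 1.005 | 1.001 | 1.004 |
| Arm only (HC 30%, UC 10%) | 0.997 | 0.997 | 0.996 | 0.997 |
| Baseline, same in both arms | 0.995 | 0.995 | 1.000 | 0.996 |
| Baseline, HC only | 0.963 | 0.964 | 0.998 | 0.997 |
| Baseline, opposite by arm | 0.930 | 0.932 | 0.995 | 0.997 |
| Unseen Week-16 score, HC only | 0.949 | 0.951 | 0.974 | 0.975 |

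Dropout was about 20% in each arm in the last four rows, so unequal rates are not needed. The two biased baseline rows match the hand calculation. In points, 0.037 × 50 = 1.85 and 0.070 × 50 = 3.5.

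**Step 4: the other direction.** When sicker UC patients leave more often, a further simulation on assumed inputs gave 1.046 with clinic-level correlation and 0.993 with the two visits correlated. Higher SGRQ is worse, so this pattern hides a benefit of coaching, whereas loss of sicker HC patients creates one. A separate simulation (330 patients, SD 20, correlation 0.6-0.75, dropout 10-15% in HC and 20-30% in UC, stronger dependence on severity in UC) gave a responder difference of 2.0-2.9 points, against −0.10 to +0.07 after regression on baseline. With equal dropout and equal dependence it gave 0.04-0.05.

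**Step 5: the efficiency claims.** Under random dropout the Monte Carlo errors, which are proportional to the SD of the log ratio, were 0.0040 (clinic level) and 0.0029 (participant level): 0.0029/0.0040 = 0.725, about a quarter lower. ANCOVA theory gives √(1 − 0.7²) = 0.714. The clinic-level model therefore forgoes the ANCOVA gain. That gain comes from the responders' own baseline scores. With a single follow-up, the normal-theory likelihood splits into a baseline part and a part for Week 16 given baseline and arm. Baseline-only participants enter only the first part, so they add nothing to the difference between arms even when the visits are correlated.

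**The case against.** The best defence is that within-participant correlation was intended. The nesting phrase can be read as repeated outcomes nested within clinics, and the asserted ANCOVA equivalence fits only a model that links the two visits. If that is what was fitted, baseline-dependent bias largely disappears (0.998 and 0.995 above). This stands as a possibility, but the plan does not say so, and the only level it names is the clinic.

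Second, every magnitude rests on assumed inputs, and the biased scenarios were chosen to have arm-specific selection. A research assistant, not the coach, administers the survey, and each completed survey is paid for, which may limit differential loss. This stands too: the figures show what could happen, not what did.

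Third, SGRQ and PACIC are secondary outcomes, and data collection ended in January 2025. Replacing the documented analysis now would be a post hoc change. That bears on how the remedy is reported, not on whether the model has the gap.

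A reader might infer more than the documents support:

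- That the analysis discards non-responders. Participants without follow-up stay in the model; what is missing is any influence of theirs on the Week-16 contrast.
- That GEE is unbiased here only if dropout is completely random. Dropout by arm alone, or by baseline equally in both arms, caused essentially no bias.
- That unequal dropout rates are themselves the problem. The problem is dependence on prognosis that differs by arm.
- That a primary outcome is shown to be biased. Receipt of medications is scored from the EHR. Table E1 does count some patient-reported items towards gap closure, so the statement that only survey outcomes are affected should be confirmed, but nothing here demonstrates bias in a primary outcome.

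**Conclusion.** The concern holds in a limited form. With correlation described only within clinics, the Week-16 survey contrast is in effect a responder comparison, and the claimed ANCOVA equivalence and power gain do not follow. The contrast is biased if dropout depends on baseline severity differently by arm: about 4-7% of the mean, roughly 2-3.5 SGRQ points at a mean of 50, under the assumed mean, SD, correlation and dropout. It is about 0 under the three benign mechanisms. PACIC was not simulated; it shares the model, so the mechanism carries over but the size does not. The planned dropout comparison neither separates the arms nor leads to any action. The weight is moderate: secondary patient-reported outcomes are affected and the remedy is cheap, but whether the actual results are biased cannot be judged from the documents.

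**What to change.** 1. State the working correlation and the missingness assumption. Correct the sentences on ANCOVA equivalence and on power so that they describe the model actually fitted.
2. For continuous scores (SGRQ and its domains, PACIC), fit the cLDA with within-participant correlation: a likelihood-based mixed model with participant and clinic effects, or a GEE with participant-level correlation that still accounts for clinic. State the effect scale, because a linear mixed model gives a difference, not a relative mean.
3. For all Week-16 survey outcomes, including the binary ones, add multiple imputation by arm or inverse-probability-of-response weights, using baseline score, diagnosis, clinic and EHR utilization.
4. Report the amount and the predictors of dropout separately by arm.
5. Add a sensitivity analysis for dropout that depends on the unobserved Week-16 score. Neither weighting nor participant-level correlation removed that bias (0.975 and 0.974).
6. Because the data are already collected, report the documented clinic-level GEE alongside and label the added analyses as added.

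The cost is wording and some extra analysis work. The baseline and EHR data needed are already held.

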### **Setting**

The PuSHCon study was conducted between October 2020 and January 2025 at ten urban Federally Qualified Health Centers (FQHCs) or “FQHC look-alikes” by the Health Services Resources and Services Administration. Eight participating study clinics were in the community and two were located at the county hospital medical campus.

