### Outcome Measures

Primary outcomes, as defined in ClinicalTrials.gov (NCT03695276) prior to the study launch, were the receipt of guideline-based care and the receipt of recommended medications. For *Receipt of guideline-based care*, we identified 13 guideline-based care recommendations (Table E1) based on international GOLD and GINA guidelines. For each participant, we identified the items for which the participant had an unmet recommendation ("care gap") at baseline. The outcome was the proportion of those care gaps that were addressed by 16 weeks, as documented in the electronic health record.

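### The first primary outcome is x closed gaps out of d, yet it is modelled as negative binomial in a GEE on ten clinics, so its confidence interval is not reliably calibrated

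*Combined protocol and SAP*

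**What the plan says.** Outcome Measures defines the endpoint as a bounded proportion: "The outcome was the proportion of those care gaps that were addressed by 16 weeks". The same section draws the gaps from a list of 13 recommendations, so d is at most 13. In Analysis Methods the denominator d "is the number of gaps in care noted over the 12-month pre-baseline", and the numerator x "is the number of these gaps that were noted as addressed during the 16-week intervention (numerator"). Hence 0 ≤ x ≤ d for every participant. For this outcome the plan "specified a negative binomial distribution for" x, with a log link and log(d) as offset.

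The general statement in Analysis Methods is that "we used generalized estimating equation (GEE) models to estimate the mean (95% CI) ratio of arm-specific rates", "while accounting for correlated outcomes within study clinics". The Setting section gives ten clinics. Four things are not stated: whether the 95% intervals use model-based or sandwich standard errors, how dispersion and scale are set, what working correlation is used, and whether any small-sample correction applies. No reason is given for choosing a negative binomial. The other primary outcome, receipt of all recommended medications, is modelled as binomial with a log link.

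**The concern.** A negative binomial is a model for unbounded counts. It gives probability to x above d, and its variance can never fall below its mean, d·p. A count of successes out of d has variance d·p(1−p) when the d items behave independently, which is below that floor. The working variance can therefore be wrong for the data at hand. If the interval relies on it, the interval inherits the error.

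The other possibility is that the interval comes from a sandwich estimator clustered on clinic. That estimator tolerates a wrong working variance, but it is known to run small with as few as ten clusters. What is at stake is the interval and p-value for a primary outcome, whose calibration would depend on software choices that the plan does not record.

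**Working it through.** **Inputs from the documents.** x ≤ d; d ≤ 13; ten clinics; 1:1 randomization within clinic; 165 patients assigned to the health coach, so about 165 in usual care is inferred. The documents give no standard error, power, closure rate or distribution of d for this outcome, so there is no stated figure to reproduce.

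**Assumed inputs.** Mean d about 5; closure rates 0.2 to 0.6; within-patient correlation ρ from 0 to 0.3.

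**Step 1: variances of x.**
- Binomial: d·p(1−p)
- Beta-binomial: d·p(1−p)[1+(d−1)ρ]
- Negative binomial: μ+αμ², with μ = d·p; its floor as α goes to 0 is the Poisson value d·p

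**Step 2: independent closures (ρ = 0).** The ratio of the model-based standard error at the floor to the true one is 1/√(1−p).

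| p | ratio | excess |
|---|---|---|
| 0.2 | 1/√0.8 = 1.118 | 12% |
| 0.3 | 1/√0.7 = 1.195 | 20% |
| 0.4 | 1/√0.6 = 1.291 | 29% |
| 0.5 | 1/√0.5 = 1.414 | 41% |

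**Step 3: where the excess vanishes.** Setting d·p(1−p)[1+(d−1)ρ] = d·p gives ρ = p/[(1−p)(d−1)]. For d = 5 this is 0.2/(0.8×4) = 0.06, 0.3/(0.7×4) = 0.11, 0.4/(0.6×4) = 0.17 and 0.5/(0.5×4) = 0.25. Above these values the true variance exceeds the floor.

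**Step 4: one scenario by hand.** 165 per arm, d = 5, closure 0.30 against 0.45. Expected closures are 165×5×0.30 = 247.5 and 165×5×0.45 = 371.25.
- Poisson-limit SE of log RR: √(1/247.5 + 1/371.25) = 0.082
- Binomial SE: √(0.70/247.5 + 0.55/371.25) = 0.066; ratio 0.082/0.066, about 1.25
- With ρ = 0.2, the variance is multiplied by 1+4×0.2 = 1.8, so SE = √(0.00431×1.8) = 0.088, now above 0.082

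**Step 5: simulation.** 300 trials per scenario, ten equal clinics, no added clinic effect, mean d = 5, dispersion estimated, scale fixed at 1, independence working correlation.

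| closure | ρ | empirical SE | model SE (coverage) | sandwich SE (coverage) |
|---|---|---|---|---|
| 0.3/0.45 | 0 | 0.064 | 0.082 (99.0%) | 0.061 (91.0%) |
| 0.4/0.6 | 0 | 0.051 | 0.071 (99.0%) | 0.047 (90.7%) |
| 0.3/0.45 | 0.2 | 0.094 | 0.088 (93.7%) | 0.082 (88.0%) |
| 0.4/0.6 | 0.2 | 0.071 | 0.071 (94.3%) | 0.066 (89.3%) |
| 0.2/0.3 | 0.3 | 0.132 | 0.130 (95.3%) | 0.124 (90.7%) |

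Over all 12 scenarios the mean log RR was 0.401 to 0.418 against a true ln(1.5) = 0.405. Sandwich coverage ran from 85% to 94%, averaging 90%. The Monte Carlo error of one such figure is √(0.9×0.1/300), about 1.7 points, so the lowest value is partly noise; the average is not.

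**Step 6: the alternatives.** A second set of simulations used 400 trials in each of 16 scenarios: 330 patients, mean d about 5.2, usual-care closure 0.3 or 0.4, RR 1.0 or 1.2, clinic SD 0.1, ρ from 0 to 0.3. Coverage of nominal 95% intervals was:
- negative binomial, dispersion near 0, fixed scale: 86.5% to 99.8%
- negative binomial GEE, uncorrected clinic sandwich: 89% to 94.5%, average 91%
- binomial, log link, estimated scale, clinic fixed effects: 92% to 96.5%, average 94.4%

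In a further run, a small-sample-corrected sandwich with t on 9 df covered 93% to 98%.

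**The case against.** The strongest defence is that the analysis is a GEE, where a sandwich standard error is the usual choice. The working variance then affects mainly efficiency, the rate ratio remains consistent, and the interval is not too wide. This stands as far as it goes. It does not make the interval sound, because the sandwich rests on ten clusters and undercovers. That shortfall is not evidence against the negative binomial: a binomial GEE clustered on clinic would share it.

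Three stronger readings are tempting, and the documents support none of them.

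- **That the interval is always too wide because x cannot exceed d.** This needs gaps to close nearly independently. The plan has one coach, one set of specialist recommendations and the patient's own primary care provider acting on all of a patient's gaps, so positive correlation is plausible. At closure 0.4, with dispersion near 0 and fixed scale, the ratio of model to true standard error fell to 0.79–0.81 at ρ = 0.3.
- **That power collapses to a few percent.** This requires the dispersion to be fixed at 1, which the plan does not say.
- **That no negative binomial route gives a correct standard error.** With 330 patients, mean d 5.6, closure 0.4, RR 1.15 and ρ = 0, estimating the scale moved the ratio of model to empirical standard error from 1.36 to 1.04 and power from 46% to 71%. Estimated scale restored coverage to about 94–96%. Much of the power loss therefore comes from a fixed scale and not from the family alone.

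**Conclusion.** The concern holds as one of calibration and specification for a primary outcome. The point estimate is not in question. The stated model does not match a bounded x out of d, and the plan leaves open every choice that would determine whether its interval is valid. Depending on those choices, the standard error may be 12% to 41% too large (fixed scale, independent closures, p from 0.2 to 0.5), about right or too small (fixed scale, correlated closures), or too small through the ten-cluster sandwich (coverage about 85% to 94%).

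Any power gain from a binomial model is conditional. With independent closures and RR 1.2, power was 64% for the fixed-scale, near-zero-dispersion negative binomial against 77% for the binomial at closure 0.3, and 78% against 92.5% at closure 0.4. At a within-patient correlation of 0.2 or more the advantage is gone. All magnitudes rest on assumed closure rates, d, ρ and clinic variation. The effect on the reported result cannot be established from the documents.

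**What to change.** Model x out of d as binomial events over trials with a log link and an estimated scale (quasi-binomial or beta-binomial). Keep arm as the effect and the rate ratio as the estimand, and include clinic, within which patients were randomized, as a fixed effect. The log(d) offset is then unnecessary. Alternatively, keep the clinic-clustered GEE but use a small-sample-corrected standard error with a t reference. Either way, state the standard error type, the handling of scale and dispersion, and the correction used.

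With arm as the only term, the Poisson-limit and log-binomial estimating equations both give the ratio of Σx/Σd between arms, so the change concerns the interval rather than the estimate. Clinic terms make it a clinic-adjusted ratio.

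Recruitment and follow-up ended by January 2025. If the results are already known, report this as a labelled sensitivity analysis beside the stated model and do not replace it.

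The cost is a few lines of plan text and one re-run. The downsides are possible log-binomial convergence problems, an interval slightly wider than the uncorrected sandwich gives, and some loss of power with the corrected GEE.

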**Table E2. Defining receipt of guideline-based medications**

Condition	Classification	Guideline for minimal medications
COPD	Prior to 2024	
	Class A	Rescue inhaler: Short acting beta agonist (SABA)
	Class B	Rescue: SABA AND Controller: Long-acting beta agonist (LABA) OR Long-acting muscarinic agent (LAMA)
	Class C	Rescue: SABA AND Controller: Long-acting muscarinic agent (LAMA)
	Class D	Rescue: Short acting beta agonist AND Controller: Long-acting muscarinic agent (LAMA) OR LAMA + LABA OR ICS + LABA
	After 2024:	
	Class B	Rescue: SABA AND Controller: LAMA AND LABA
	Class E (formerly C/D)	Rescue: SABA AND Controller: LABA AND LAMA

Asthma	Steps 1-2 (formerly intermittent or mild persistent asthma)	SMART Therapy: Inhaled corticosteroid (ICS) + LABA as needed OR Rescue: ICS + SABA together
	Step 3 (formerly moderate persistent asthma)	SMART Therapy with low dose ICS + LABA
	Steps 4 – 5 (formerly severe persistent asthma)	SMART Therapy with moderate dose ICS for persistent asthma)

Pre-specified secondary outcomes included the proportion of patients in each arm who received chronic lung disease education, defined as referral to any class or one-on-one education on chronic lung conditions or patient-reported receipt of education on identifying and responding to signs of exacerbations, staying active, or breathing training. In addition, we measured several patient-reported outcomes, including disease-specific quality of life, as measured by the St. George Respiratory Questionnaire (SGRQ) and symptoms, as measured by the symptom subscale of the SGRQ. Patient-reported quality of care was measured using the short form of the Patient Assessment of Chronic Illness Care (PACIC) (mean item score 1-8). Self-reported adherence to inhaler therapy was defined as the proportion of patients taking all doses of controller medications as prescribed in at least five of the last seven days. For the intervention arm, provider acceptance of recommended care was defined as the proportion of PSNP recommendations for which the provider took action, including placing of referrals, orders for new prescriptions, or approval for the health coach to follow up.

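### The plan says the SGRQ and PACIC models estimate geometric means, but the log-link model it specifies estimates arithmetic means and their ratio

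*Combined protocol and SAP*

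**What the plan says.** The general paragraph of Analysis Methods states that "we used generalized estimating equation (GEE) models", and that for continuous outcomes these estimate a ratio of "geometric means (for continuous outcomes) and to generate 2-sided p-values, while accounting for correlated outcomes within study clinics".

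The SGRQ paragraph of the same section gives the model. The score, written z, is modelled "as a function of time and time\*arm, used a log link, and specified that" y "has a negative binomial distribution". The symbol thus changes from z to y within one sentence, and neither is defined for SGRQ. The next sentence reads "The model estimates geometric means (95% CI) and estimates the relative mean (RM) (95% CI", comparing HC with UC at Week 16.

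The paragraph gives the SGRQ total a range of 0 to 100. It applies the same method to the three domains and names PACIC as another outcome using the model. Outcome Measures, in the secondary-outcome text after Table E2, describes PACIC as a "mean item score 1-8".

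The documents do not state whether standard errors are sandwich or model-based, how the negative binomial dispersion is set, which working correlation is used, or whether there is a small-sample correction for ten clinics.

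**The concern.** The plan names one estimand and specifies a model for another. A reader or meta-analyst who trusts the text would take the reported means and RM as geometric. A geometric ratio responds to changes in spread and to low scores in a way that an arithmetic ratio does not, so the difference is one of meaning as well as wording.

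A second, weaker issue concerns the variance. The negative binomial describes unbounded counts, and its variance cannot fall below its mean. It is an unnatural working variance for a bounded mean item score such as PACIC. If the standard errors rested on it, intervals could be too wide.

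Finally, a ratio of scores cannot be read directly as a change in points on the 0-100 SGRQ scale, although the reference list includes a paper on the minimal clinically important difference for that scale.

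**Working it through.** The plan gives no mean, SD or sample-size figure for SGRQ or PACIC, so there is no figure of its own to reproduce. The scales, link, distribution, model terms and ten clinics come from the documents. All means, SDs, correlations and missingness below are assumptions.

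**1. What the model estimates.** With a log link, log E(Y) = b0 + b1·time + b2·time·arm. Hence:
- common baseline mean = exp(b0)
- UC mean at Week 16 = exp(b0 + b1)
- HC mean at Week 16 = exp(b0 + b1 + b2)
- RM = exp(b2), a ratio of arithmetic means

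A geometric mean is exp(E[log Y]), which requires a model of log Y. A score of 0 has no logarithm.

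**2. Size of the difference.** Scaled-beta scores were simulated, 200,000 per arm, and fitted with a two-arm log-link negative binomial model.

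| Assumed scenario (UC, HC) | Fitted means | RM | Arithmetic ratio | Geometric means | Geometric ratio |
|---|---|---|---|---|---|
| SGRQ 45, 41; SD 20 | 45.05, 40.97 | 0.909 | 0.909 | 39.6, 35.0 | 0.884 |
| SGRQ 45, 45; SD 15, 22 | 44.99, 45.04 | 1.001 | 1.001 | 42.2, 38.1 | 0.903 |
| PACIC 4.0, 4.5; SD 1.5 | 4.00, 4.50 | 1.125 | 1.125 | 3.69, 4.22 | 1.142 |

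The fits were the same at dispersion k = 0.175 and k = 1. In every scenario the model returned the arithmetic means.

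**3. Model-based standard errors.** For a simple comparison of means, the ratio of model-based to true SE is sqrt[(m + k·m²)/SD²].
- PACIC, mean 4, at the smallest possible variance (k = 0): SD 1 gives sqrt(4/1) = 2.0; SD 1.5 gives sqrt(4/2.25) = 1.33; SD 2 gives sqrt(4/4) = 1.0.
- SGRQ, mean 45, SD 20: matching the variance gives k = (400 − 45)/2025 = 0.175 and a ratio of 1.0. With k fixed at 1 the ratio is sqrt(2070/400) = 2.27.

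**4. Coverage in the planned structure.** A cLDA GEE was simulated with no arm effect, 10 clinics of 33 patients, 10% missing at Week 16, between-visit correlation 0.6, ICC 0.03 and 250 replicates. The total of 330 assumes a UC arm equal to the 165 patients assigned to the coach. Ranges cover independence and exchangeable working correlation.

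| Case | Model-based | Sandwich | Bias-reduced sandwich |
|---|---|---|---|
| SGRQ, k = 0.175 | 95.2–96.0% | 89.2–90.4% | 92.8% |
| SGRQ, k = 1 | 100% | 90.0–91.6% | 94.0–94.4% |
| PACIC, SD 1.5, k near 0 | 98.8–99.6% | 92.4–93.6% | 93.6–94.8% |

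Monte Carlo error is about 1.5 to 2 points. For SGRQ, sandwich coverage was similar at both values of k. Its shortfall below 95% reflects having ten clusters, not the negative binomial choice.

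**The case against.** The strongest defence is that GEE needs only a correct mean model. The named distribution sets the working variance, so the arm means are estimated consistently even for bounded, non-integer scores. The model also has only three fitted means, so fitted values outside the scale are not a practical concern, and a Gaussian model is unbounded too. All of this stands.

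A reader might infer that the SGRQ and PACIC intervals are wrong. The documents do not support that. Sandwich standard errors do not depend on the negative binomial variance, and the text does not say that model-based ones were used. Even with model-based errors, PACIC intervals are too wide only if the variance is below the mean, and no PACIC SD is given. For SGRQ, the problem disappears when dispersion is matched to the data.

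It is also fair to say that the ratios need not differ: an effect that multiplies every score by the same factor gives identical arithmetic and geometric ratios. The gap depends on the shape of the effect, so the figures above are illustrations.

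One might suppose that z is a log-transformed score. That would rescue the label only with an identity link; the stated log link and count distribution contradict it.

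Lastly, a ratio of means is a legitimate effect measure. Recruitment and follow-up ran to January 2025 and the document is dated September 2025, so replacing the main model now would invite the charge of a data-driven change. That argues for correcting the label and keeping the model.

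**Conclusion.** The label is wrong for the model as written: the stated GEE estimates arithmetic means and their ratio. This follows from algebra and rests on no assumed value. How far the two ratios part does rest on assumptions: 0.909 against 0.884 in one plausible SGRQ case, and 1.00 against 0.90 when means are equal but spreads differ.

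The variance point is conditional. At an assumed PACIC mean of 4, model-based standard errors would be 1.33 times too large at SD 1.5 and correct at SD 2. With sandwich standard errors this inflation does not arise.

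The issue is confined to secondary outcomes. A reader might extend it to the primary guideline-care outcome, which also uses a log-link negative binomial model. That outcome is a count with an offset and is reported as a rate ratio, not as a geometric mean, so the labelling error does not reach it.

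**What to change.** - In both places in Analysis Methods, replace geometric means with means, and define RM as the ratio of arithmetic means at Week 16, HC to UC.
- Use one defined symbol for the score in place of z and y.
- State that standard errors are sandwich, so that inference does not rest on the negative binomial variance. With ten clinics, a bias-reduced version is preferable. State the dispersion and the working correlation as well.
- Report the Week-16 difference in points with a 95% CI. It can come from the same fit as exp(b0 + b1)·[exp(b2) − 1]; in the first scenario above, 40.97 − 45.05 = −4.08 points. Alternatively, add a supportive Gaussian identity-link cLDA, labelled as added after the fact.

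If the analysis was in fact run on log scores, the text needs the opposite correction: state the transformation, the identity link and the rule for zeros.

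The cost is a few lines of wording, possibly a re-run to change the standard errors, and one extra reported estimate per outcome.
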